8.2.1. Inclusion criteria

Physician/Clinician Participants

Participating sites must undergo a contracting procedure and agree to follow the study protocol as well as all terms of the study contract. Participating sites will be led by a physician / clinician (e.g. nurse, nurse practitioner, physician assistant, etc.) who will serve as that site's PI/sub-PI. The participating PI/sub-PI must meet all the following inclusion criteria to participate in the study:

- Must be a healthcare provider with at least 60% of time spent in direct patient care;
- Board-certified or eligible with a Specialty in Hematology or Hematology-Oncology (if hematologist-oncologist, at least 10% practice is dedicated to treatment of hemophilia);
- Currently manages at least 10 hemophilia A and/or B patients;
- Must not be on the FDA debarment list.

Patient Participants

Participants must meet all of the following inclusion criteria to be eligible for inclusion in the study:

- Willing and able to provide informed consent.
- Diagnosed with hemophilia A or B.
- Current disease severity is either moderately severe or severe with a clotting factor level of $\leq 5\%$.
- If suffering from hemophilia A, must be currently taking Xyntha (or another standard half-life treatment), Adynovate or Eloctate for at least six months.
 - If currently taking Adynovate or Eloctate, must have been switched from a standard half-life treatment and had been on that prior treatment for at least six months.
- If suffering from hemophilia B, must be currently taking BeneFIX or Alprolix for at least six months.
 - If currently taking Alprolix, must have switched from BeneFIX and had been on that prior treatment for at least six months.
- Infuse at least 3 times per month

1. In the event of a caregiver responding on behalf of the patient, the above inclusion criteria will be applied for the patient for whom the caregiver is responding.

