8.2.2. Exclusion criteria

Patient Participants

Currently enrolled in a clinical trial and/or using investigational product for the treatment of his or her hemophilia

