Appendix 2. FACTOR USE BEHAVIOR QUESTIONS

In responding to this question, please think about what ‘you did’ / ‘the child with hemophilia did’ over the past month.

For the factor replacement therapy ‘you use’ / ‘the child with hemophilia uses’ to prevent and control bleeds, over the past month, how many times did ‘you’ / ‘the child with hemophilia had to’ **use an extra infusion for each of the following reasons?**

Felt pain which I thought was a bleed	Never	1 time	2 times	3 times	4 times or more
Bleeding episode	Never	1 time	2 times	3 times	4 times or more
Wanted additional protection before engaging in a sport or other impact activity	Never	1 time	2 times	3 times	4 times or more
Want extra protection for some another reason	Never	1 time	2 times	3 times	4 times or more
Other reason not listed	Never	1 time	2 times	3 times	4 times or more

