##### *Patient Treatment Pattern (from patient chart)*

- Current and previous hemophilia treatment
- Reasons for discontinuation
- Duration of treatment used
- Whether prescription was prophylaxis or on-demand
- Number of infusions per month prescribed

Protocol # B1821056  
Statistical Analysis Plan

- Frequency of doctor visits for management of hemophilia

*Patient Demographics (from patient chart)*

- Age
- Sex
- Race
- Weight
- Height
- Health insurance type

*Patient Clinical Profile (from patient chart)*

- Age of diagnosis
- Primary symptoms
- Disease severity
- Joint health score
- Comorbidities

Patient Participants (self-reported or caregiver reported):

*Patient Demographics*

- Sex
- Age
- Race/ethnicity
- Marital status
- Household income
- Education\*
- Employment status\*
- Health insurance type

Protocol # B1821056  
Statistical Analysis Plan

- Healthcare insurer
- Pharmacy insurer

\*In the case of caregivers responding, caregiver's education and employment will also be collected.

*Patient Clinical Profile*

- Disease severity
- Clotting factor level

*Patient Treatment*

- When are infusions done
- Number of infusions in a typical month
- Previous and current hemophilia treatments
- Duration of previous and current hemophilia treatments used
- Recent factor use behavior
- Whether participated in clinical trials within the past 12 months

*Physician Patient Relationship*

- Patient's relationship with his/her physician in regards treatment decisions for hemophilia rated as either paternalistic, informative, interpretive, or deliberate depending upon which relationship description the patient selects.

*Validated Scales for Health-Related Quality of Life*

*Global health-related quality of life scales*

36 Item Short Form Health Survey (SF-36; adult): The SF-36v2 is a multipurpose, generic health status instrument comprised of 36 questions. These items map onto eight health domains: physical functioning, physical role limitations, bodily pain, general health, vitality, social functioning, emotional role limitations, and mental health. In addition to these eight health domains, there are two component summary scores: the physical component summary (PCS) and the mental component summary (MCS).

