When diagnosed with hemophilia	Infancy 0-12 months							
	Toddler 1-3 years							
	Preschool 3-5 years							

Protocol # B1821056  
 Statistical Analysis Plan

**Table 3. Example bivariate table: Patient health characteristics, disease characteristics, and treatment history among hemophilia A patients by standard half-life vs. extended half-life treatment (from patient chart). Note: a similar table would be created for hemophilia B patients.**

	Treatment Group							
	Standard Half-Life		Extended Half-Life		Total			
	% / Mean	N/ SD	% / Mean	N/ SD	% / Mean	N/ SD		
Grade school 5-12 years Teen 12-18 years Young adult 18-21 years <21 years Don't know								
Comorbidities	Joint disease High blood pressure High cholesterol Heart disease Diabetes HIV Hepatitis Other (specify) None of above							
Currently taking medication for joint disease?	Yes No							
Current disease severity	Moderate hemophilia (1-5% factor level) Severe hemophilia (Less than 1% factor level)							
Current primary symptoms	Excessive bleeding after cuts, injuries, or medical procedures Unexplained nosebleeds Excessive bruising Joint pain, swelling, or tightness Blood in stool or urine Other None of the above							
Current joint	Score							

Protocol # B1821056  
 Statistical Analysis Plan

**Table 3. Example bivariate table: Patient health characteristics, disease characteristics, and treatment history among hemophilia A patients by standard half-life vs. extended half-life treatment (from patient chart). Note: a similar table would be created for hemophilia B patients.**

		Treatment Group							
		Standard Half-Life		Extended Half-Life		Total			
		% / Mean	N/ SD	% / Mean	N/ SD	% / Mean	N/ SD		
health score	Don't know								
Joint health score system	Hemophilia Joint Health Score (HJHS)  World Federation of Hemophilia (WFH) score  Other joint scoring system (specify)								
Current factor	Advate  Adynovate  Afstyla  Eloctate  Helixate FS  Hemofil M  Kogenate FS  Kovaltry  Monoclate-P  Novoeight  Nuwiq  Recombinate  Xyntha solofuse  Other, specify								
How factor prescribed	Prophylactically  On-demand  Both prophylactically and on-demand								
Duration of current factor prescribed									
Number of infusions per month									
Prior treatment	Advate  Adynovate  Afstyla  Eloctate  Helixate FS  Hemofil M								

Protocol # B1821056  
 Statistical Analysis Plan

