**Table 3. Example bivariate table: Patient health characteristics, disease characteristics, and treatment history among hemophilia A patients by standard half-life vs. extended half-life treatment (from patient chart). Note: a similar table would be created for hemophilia B patients.**

	Treatment Group						p-value	
	Standard Half-Life		Extended Half-Life		Total			
	% / Mean	N/ SD	% / Mean	N/ SD	% / Mean	N/ SD		
Kogenate FS								
Kovaltry								
Monoclate-P								
Novoeight								
Nuwiq								
Recombinate								
Other, specify								
Was not taking another treatment previously								
Duration of former factor prescribed								
Reasons for discontinuation	Cost/insurance coverage issues							
	[IF PATIENT IS UNDER 18] Patient developed inhibitors to treatment							
	Doctor recommendation							
	Patient preferred a different infusion frequency							
	Other							
	Don't know							
Frequency of visits (non-infusion)	Several times a month							
	Once a month							
	Every three months							
	Every six months							
	Once a year							
	Less than once a year							

Protocol # B1821056  
 Statistical Analysis Plan

**Table 4. Example bivariate table. Patient health characteristics, disease characteristics, and treatment history among hemophilia A patients by standard half-life vs. extended half-life treatment (patient-reported). Note: a similar table would be created for hemophilia B patients.**

		Treatment Group							
		Standard Half-Life		Extended Half-Life		Total			
		% / Mean	N/ SD	% / Mean	N/ SD	% / Mean	N/ SD		
Severity	Mild hemophilia Moderate hemophilia Moderately severe hemophilia Severe hemophilia								
Clotting factor level	6% to 40% 1% to 5% Less than 1%								
Current treatment	Advate Adynovate Afstyla Eloctate Helixate FS Hemofil M Kogenate FS Kovaltry Monoclate-P Novoeight Nuwiq Recombinate Xyntha solofuse Other, specify								
Duration of current factor prescribed									
When infuse	On regular basis to prevent bleeding episodes Whenever or as needed when there is a bleeding episode Both, on a regular basis to prevent bleeding episodes as well as whenever as needed when there is a bleeding episode								
Prior treatment	Advate Adynovate								

Protocol # B1821056  
 Statistical Analysis Plan

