**Table 4. Example bivariate table. Patient health characteristics, disease characteristics, and treatment history among hemophilia A patients by standard half-life vs. extended half-life treatment (patient-reported). Note: a similar table would be created for hemophilia B patients.**

	Treatment Group							
	Standard Half-Life		Extended Half-Life		Total			
	% / Mean	N/ SD	% / Mean	N/ SD	% / Mean	N/ SD		
Afstyla								
Eloctate								
Helixate FS								
Hemofil M								
Kogenate FS								
Kovaltry								
Monoclate-P								
Novocight								
Nuwiq								
Recombinate								
Other, specify								
Was not taking another treatment previously								
Duration of former factor prescribed								
Clinical trials for receiving treatment	Yes							
	No							

**Table 5. Example bivariate table. Health-related quality of life among hemophilia A patients by standard half-life vs. extended half-life treatment (patient-reported). Note: a similar table would be created for hemophilia B patients.**

	Treatment Group							
	Standard Half-Life		Extended Half-Life		Total			
	Mean	SD	Mean	SD	Mean	SD		
for adults								
SF-36 Physical Component Summary Score								
SF-36 Mental Component Summary Score								
HAEM-A-QOL)								
caregiver reported for child								
SF-10 Physical summary score								
SF-10 Psychosocial health summary score								
HAEMO-QOL								

Protocol # B1821056  
 Statistical Analysis Plan

**Table 6. Example bivariate table. Patients' attitudes on factor use and physician relationship among hemophilia A patients by standard half-life vs. extended half-life treatment. Note: a similar table would be created for hemophilia B patients.**

		Treatment Group						p-value	
		Standard Half-Life		Extended Half-Life		Total			
		%	N	%	N	%	N		
Frequency of extra infusion used	Never								
	2 times								
	3 times								
	4 times or more								
Reasons for using extra infusion	Bleeding episode								
	Wanted additional protection before sport/activity								
	Felt pain (thought it was bleed)								
	Wanted extra protection for no specific reason								
Frequency of dose higher than prescribed	Never								
	1-2 times								
	3-4 times								
	5-6 times								
	7 or more times								
Reasons for higher dosing	Wanted additional protection before sport/activity								
	Felt pain (thought it was bleed)								
	Wanted extra protection for no specific reason								

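### SAP Table 6 compares extra infusions between half-life groups over all patients, although for on-demand-only patients, who are eligible, an extra infusion has no defined meaning

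*SAP*

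**What the plan says.** **Who can enter.** Protocol 8.2.1 sets a frequency threshold, "Infuse at least 3 times per month", and no regimen restriction. The one patient exclusion in Protocol 8.2.2 is "Currently enrolled in a clinical trial and/or using investigational product". SAP section 2.2 repeats both. The plan expects mixed regimens: SAP 4.1 lists "Whether prescription was prophylaxis or on-demand" as a chart variable. SAP Table 3 has prophylaxis, on-demand and "Both prophylactically and on-demand" as separate categories, and patient-reported Table 4 has "Whenever or as needed when there is a bleeding episode" as its own category.

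**What is asked.** Protocol Appendix 2 concerns factor used "to prevent and control bleeds, over the past month", and asks how often the respondent had to "use an extra infusion for each of the following reasons". The reasons include a bleeding episode and pain thought to be a bleed, alongside protection before sport and other protection. Each reason is answered from never to four times or more. *Extra* is not defined, and no not-applicable option or regimen filter is shown.

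**What is analysed.** SAP Table 6 tabulates "Frequency of extra infusion used", and the reasons, by half-life group only, with a p-value column. SAP 6.2.2 describes the comparison as unadjusted. Extra infusions are not among the modelled outcomes in SAP 6.2.3 or Table 8.

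**The concern.** For a patient on prophylaxis, an infusion outside the schedule is extra. For a patient treated only on demand there is no schedule, and infusing for a bleed is the prescribed regimen. The item gives such a patient no clear way to answer. Counting bleed infusions can place the patient in the top categories without any infusion beyond the regimen; answering never puts the patient at the bottom. Either answer is a reasonable reading of the question.

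The SAP introduction says that the sponsor seeks evidence on whether extended half-life products are dosed more often than labelled. Table 6 is the only table shell that shows infusions beyond schedule together with the reasons for them. A difference in its frequency row could be read as a difference in use beyond the regimen when it reflects only how many patients in each group are treated on demand. No later model adjusts this row for regimen.

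**Working it through.** The documents give no figure for this row. The only planning input used is the group size, 75 versus 75. Its stated detectable effect reproduces: (1.960 + 0.842) × √(2/75) = 0.457 by the normal approximation and 0.460 by the noncentral t, against Cohen's d = 0.46. The point does not depend on it.

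**Step 1: categories.** An on-demand-only patient at the entry minimum, with three infusions in the recall month all for bleeds and all reported as extra, is in the *3 times* category. With four or more, the patient is in *4 times or more*. Neither case includes an infusion beyond the regimen.

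**Step 2: assumptions (not in the documents).** Every on-demand patient scores 3 or more. Extra infusions on prophylaxis are Poisson with mean 0.5 in both groups, so there is no true difference. The on-demand share s is varied.

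**Step 3: level.** P(Poisson(0.5) ≥ 3) = 1.4%. The scored share at 3 or more is s + (1 − s) × 0.0144:

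- s = 5%: 0.05 + 0.95 × 0.0144 = 6.4%
- s = 10%: 0.10 + 0.90 × 0.0144 = 11.3%
- s = 20%: 0.20 + 0.80 × 0.0144 = 21.2%
- s = 30%: 0.30 + 0.70 × 0.0144 = 31.0%

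So 10% on-demand in both groups turns a true 1.4% into 11.3% in each, with no group difference.

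**Step 4: group comparison.** SAP 6.1.2 names chi-square for categorical variables, while SAP 6.2.2 names one-way ANOVA for Tables 3 to 7, so both were simulated. The setting is 75 per group, a 5% level and the five answer options of Appendix 2. On-demand patients are either split evenly between the top two categories or all placed in the top one. Rejection rates with no true difference:

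| On-demand share, group 1 vs group 2 | Chi-square | ANOVA on the 0–4 score |
|---|---|---|
| Equal (10% or 20% in both) | about 4–5% | about 5% |
| 20% vs 15% | about 8% | 10–11% |
| 10% vs 5% | 9–11% | 14–15% |
| 20% vs 10% | 21–24% | 30–34% |
| 15% vs 5% | 27–32% | 36–40% |
| 30% vs 10% | 66–71% | 78–81% |

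Ranges cover the two placements and simulation error.

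**Step 5: the other reading.** If on-demand patients all answer never, the row is diluted instead. The share on prophylaxis with any extra infusion is 1 − e^(−0.5) = 39.3%. With 20% on-demand, the pooled share is 0.80 × 39.3% = 31.5%. The pooled row is then wrong in the opposite direction.

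**The case against.** **The item may not be misread.** It asks about an extra infusion, so on-demand patients may answer never. The entry threshold is not tied to the recall month, and bleed infusions may be divided between the pain and bleeding rows. Appendix 2 shows only part of a questionnaire that the protocol's document list gives as still in design; the higher-dose item of Table 6, for example, is not in it. A filter could exist. All of this stands. A reader might infer that the item necessarily scores on-demand patients at the top, but the documents support only that it can. What remains is that neither document states a filter, and a row whose meaning depends on how each respondent reads *extra* should not be pooled across regimens.

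**Size.** A reader might cut the answers at 3 or more and apply a two-proportion test, which gives 38%, 49% and 86% rejection at 20% vs 10%, 15% vs 5% and 30% vs 10%. The SAP plans no such cut, and its own tests give lower rates. Nor do the documents show that on-demand shares differ, or in which direction. At equal shares there is no excess of false differences. Tables 3 and 4 also show regimen by group, so a marked imbalance would be visible. It would not be removed from Table 6.

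**Reasons are already listed apart.** Table 6 separates bleeding from sport and other protection in its reasons rows. That helps, but the frequency row is still pooled across reasons and regimens, and the SAP gives no rule for combining the per-reason counts into it.

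**Importance.** Table 6 is an unadjusted example shell about attitudes to factor use. The modelled dosing outcome is infusions per month. A reader might infer that the main comparison is compromised. The documents do not support that, because extra infusions are not a Table 8 outcome.

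**Conclusion.** The point holds for the extra-infusion rows of Table 6. The documents establish that on-demand-only patients are eligible, that the question shown gives them no defined meaning of *extra*, and that the comparison is made by half-life group alone. The pooled level can be inflated in both groups, or diluted if on-demand patients answer never.

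A false group difference needs unequal on-demand shares. Under the assumptions in the working, the planned tests reject in about 5% of studies at equal shares and in 66–81% at 30% versus 10%, with smaller imbalances in between. These rates are illustrations. They rest on an assumed on-demand share, on every on-demand patient scoring 3 or more, and on the Poisson mean of 0.5, none of which the documents give. The consequence is confined to a supporting table, but one that bears on the study's stated hypothesis.

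**What to change.** In SAP 6.2.2 and the Table 6 shell:

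1. Run the group comparison of the extra-infusion rows among patients whose regimen is prophylaxis or both. Regimen is available from the chart (*How factor prescribed*, Table 3) and from the patient (*When infuse*, Table 4). State which one classifies the patient and use the other as a check.
2. Show on-demand-only patients as a separate descriptive line, without a group test.
3. Report infusions for a bleed or suspected bleed separately from discretionary ones (sport, other protection), and keep both sets of rows. Bleed infusions on prophylaxis can be truly beyond schedule, so conclusions should not rest on the discretionary rows alone. For patients prescribed both regimens, bleed treatment is part of the prescription, which is why the two sets need separate interpretation.

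Regimen and per-reason counts are already collected, so the change is to SAP wording and one table shell. The cost is that the number analysed in these rows falls by the on-demand share, which need not be small: at 30% it removes about 22 of 75 (0.30 × 75 = 22.5).

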### 6.2.3. Multivariable Analyses

For hemophilia A and hemophilia B cohorts separately, multivariable regression models will be conducted with treatment group (standard half-life vs. extended half-life) as the predictor of each outcome (ie, number of infusions, health-related quality of life, healthcare resource utilization, total healthcare costs, total Rx costs, hemophilia healthcare costs, hemophilia Rx costs) adjusting for the demographic and health history variables that have been identified as relevant covariates in bivariate analyses.

Generalized linear models will be used specifying the appropriate distribution (ie, negative binomial for skewed variables such as healthcare resource use and cost variables; identity link function for normally distributed variables such as health-related quality life). A regression summary results table with adjusted means, 95% CIs, standard errors, and p-values will be produced ([Table 8](#)).

**Table 8. Example regression summary table. Outcomes among hemophilia A patients by standard half-life vs. extended half-life treatment (adjusted for covariates). Note: a similar table would be created for hemophilia B patients.**

Outcome	Standard Half-Life				Extended Half-Life				p-value
	Mean	SE	Lower 95% CI	Upper 95% CI	Mean	SE	Lower 95% CI	Upper 95% CI	
Number of infusions per month									
SF-36 MCS/ SF-10 psychosocial									
SF-36 PCS / SF-10 physical									
HEAM-A-QOL / HAEMO-QOL									
Total Healthcare visits									
Total Healthcare costs									
Total Rx costs									
Hemophilia healthcare visits									
Hemophilia healthcare costs									
Hemophilia Rx costs									

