7. RESEARCH QUESTION AND OBJECTIVES

The study's primary objective is to compare the dosing and resource utilization patterns of standard half-life treatments vs. extended half-life treatments for the management of hemophilia A and B

- Specifically, the dosing and resource utilization patterns of Xyntha (or other standard half-life treatments) vs. Adynovate or Eloctate will be assessed for treatment of hemophilia A
- And similarly, the dosing and resource utilization patterns of BeneFIX (standard half-life) vs. Alprolix (extended half-life) will be assessed for treatment of hemophilia B

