### Physician/Clinician Participants Inclusion Criteria

Participating sites must undergo a contracting procedure and agree to follow the study protocol as well as all terms of the study contract. Participating sites will be led by a physician / clinician (eg, nurse, nurse practitioner, physician assistant, etc.) who will serve as that site's PI/sub-PI. The participating PI/sub-PI must meet all the following inclusion criteria to participate in the study:

- Must be a healthcare provider with at least 60% of time spent in direct patient care
- Board-certified or eligible with a Specialty in Hematology or Hematology-Oncology (if hematologist-oncologist, at least 10% practice is dedicated to treatment of hemophilia)
- Currently manages at least 10 hemophilia A and/or B patients
- Must not be on the FDA debarment list

Protocol # B1821056  
Statistical Analysis Plan

Patient Participants Inclusion Criteria

Participants must meet all of the following inclusion criteria to be eligible for inclusion in the study:

- Willing and able to provide informed consent
- Diagnosed with hemophilia A or B
- Current disease severity is either moderately severe or severe with a clotting factor level of  $\leq 5\%$
- If suffering from hemophilia A, must be currently taking Xyntha (or another standard half-life treatment), Adynovate or Eloctate for at least six months.
  - If currently taking Adynovate or Eloctate, must have been switched from a standard half-life treatment and had been on that prior treatment for at least six months.
- If suffering from hemophilia B, must be currently taking BeneFIX or Alprolix for at least six months.
  - If currently taking Alprolix, must have switched from BeneFIX and had been on that prior treatment for at least six months.
- Infuse at least 3 times per month

In the event of a caregiver responding on behalf of the patient, the above inclusion criteria will be applied for the patient for whom the caregiver is responding.

Patient Participants Exclusion Criteria

Currently enrolled in a clinical trial and/or using investigational product for the treatment of his or her hemophilia

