**Health Insurance Claims Data Submitted by Patients**

- Total services and healthcare costs (healthcare visits, factor)
- Hemophilia-specific services and costs (healthcare visits, factor)

An allocation algorithm for determining how cost groupings will be defined will be developed with discussion with Pfizer.

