Physician relationship	The physician is the professional; 'I' / 'we' follow his/her recommendations. 'I' / 'We' see the physician as the expert who knows what's best for 'me' / 'my child'. The physician makes the final decision.								

Protocol # B1821056  
Statistical Analysis Plan

The physician informs 'me' / 'me and my child' of the different treatment plans available to 'me' / 'my child' and lets 'me' / 'us' select the final treatment. The physician provides technical expertise but 'I' / 'we' make the final decision on treatment.							
The physician works with 'me' / 'me and my child' to understand 'my' / 'our' values and what 'I' / 'we' want out of the treatment and then discusses the different treatment options available to 'me' / 'us' based on 'my' / 'our' needs before we make the joint decision for 'me' / 'my child'. 'I' / 'We' see the physician as a counselor.							
The physician works with 'me' / 'us' to understand 'my' / 'our' values and what 'I' / 'we' want out of the treatment, and goes over all 'my' / 'our' treatment options and his/her recommendations so that 'I' / 'we' can make the best possible decision. 'I' / 'We' see the physician as a teacher or friend.							

**Table 7. Example bivariate table. Healthcare resource use and associated costs among hemophilia A patients by standard half-life vs. extended half-life treatment (insurance-claims). Note: a similar table would be created for hemophilia B patients.**

	Treatment Group						p-value	
	Standard Half-Life		Extended Half-Life		Total			
	Mean	SD	Mean	SD	Mean	SD		
Total number of healthcare visits								
Total number of healthcare costs								
Total Rx costs								
Total number of Hemophilia-specific visits								
Total number of Hemophilia-specific costs								
Total Hemophilia Rx costs								

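### Claims visits and costs are compared by current treatment with no claims period and no on-product rule, so pre-switch claims can count as extended half-life use

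*SAP*

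**What the plan says.** The primary objective in Protocol 7, repeated in SAP 2.3, is to "compare the dosing and resource utilization patterns of standard half-life treatments vs. extended half-life treatments". The resource-use part comes from claims that patients submit.

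- **Outcomes.** SAP 4.1 defines them as totals, for example "Total services and healthcare costs (healthcare visits, factor"), plus the hemophilia-specific equivalents. One item is left open: "An allocation algorithm for determining how cost groupings will be defined will be developed with discussion with Pfizer". That concerns cost categories, not dates or exposure.
- **Unadjusted comparison.** SAP 6.2.2 and Table 7 compare such rows as "Total number of healthcare visits" between groups.
- **Adjusted comparison.** In SAP 6.2.3, "multivariable regression models will be conducted with treatment group (standard half-life vs. extended half-life) as the predictor of each outcome", with covariates and a choice of distribution. For the claims outcomes the wording is "healthcare resource utilization, total healthcare costs, total Rx costs, hemophilia healthcare costs, hemophilia Rx costs) adjusting for the demographic and health history variables". No offset or person-time term is named. Table 8 scales one row by time, "Number of infusions per month"; its six claims rows carry no time unit.
- **Who is in the EHL group.** SAP 2.2 requires at least six months on the current product. Hemophilia A patients on Adynovate or Eloctate "must have been switched from a standard half-life treatment and had been on that prior treatment for at least six months". Alprolix patients must likewise have come from BeneFIX.
- **Nearest thing to a window.** Protocol 8.9 mentions 12 months, but only when describing the patient self-report that claims replace.
- **Data already planned.** Date of service will be extracted from claims (Protocol 8.4), and treatment duration is collected from the chart and the patient (SAP 4.1).

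**The concern.** The treatment variable describes what a patient takes on the survey date, whereas the claims describe a past period of unstated length. For a patient who switched seven months ago, a 12-month claims file holds five months of SHL use, all of which the stated model assigns to EHL. The eligibility rules put only switchers in the EHL arm, so the mixing is built into that arm. They create no matching problem in the SHL arm.

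Six of the ten Table 8 outcomes are claims-based, and Protocol 6 and SAP 2 ask whether EHL products cost payors more. How far the estimate is diluted depends on a window the analyst would choose after seeing the claims. Infusions per month are not affected.

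**Working it through.** The plan gives no figure on this point. Its one sample-size figure reproduces: for 75 vs 75, (1.960 + 0.842) × √(2/75) = 0.457, or 0.460 with the t distribution, against the stated d = 0.46. It is not in dispute.

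**Assumptions, none stated in the documents.** A common 12-month window; constant monthly rates on each product; pre-switch use at the SHL arm's rate; a direct switch; time on product unrelated to level of use and spread evenly from six months to the longest time possible. Six months on the current product plus six on the prior one means a 12-month window reaches back only into SHL use.

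**One patient.** With a share f of the window on EHL and a true ratio R, the contribution is f·R + (1 − f). At six months on product, f = 0.5: R = 1.5 contributes 1.25, and R = 0.7 contributes 0.85.

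**Arm level.** Let p be the share of EHL patients with 6 to 12 months on product. Their mean f is 0.75, so the arm's on-product share is k = 1 − 0.25p and the observed ratio is 1 + (R − 1)k.

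**Longest time on product, M.** Protocol 6 dates approval to March 2014 for Alprolix, 2014 for Eloctate and 2015 for Adynovate (no month for the last two). Protocol 5 runs data collection from April to December 2017. An even spread gives p = 6/(M − 6).

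| Product | M, months | p | k | R = 1.5 appears as |
|---|---|---|---|---|
| Alprolix | 37 to 45 | 0.194 to 0.154 | 0.952 to 0.962 | 1.476 to 1.481 |
| Eloctate | 28 to 47 | 0.273 to 0.146 | 0.932 to 0.963 | 1.466 to 1.482 |
| Adynovate | 16 to 35 | 0.600 to 0.207 | 0.850 to 0.948 | 1.425 to 1.474 |

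The SAP pools Eloctate and Adynovate, so the last two rows are only steps to the hemophilia A result. With an assumed equal mix, k runs from (0.932 + 0.850)/2 = 0.891 to (0.963 + 0.948)/2 = 0.956, and 1.5 appears as 1.446 to 1.478.

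**Sensitivity to the window.** With six months, k = 1 and there is no dilution. With 24 months, the mean of min(1, t/24) is 0.782 to 0.827 for Alprolix, so 1.5 appears as 1.39 to 1.41. This shows how the bias grows; no section suggests 24 months.

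**Precision cost of a remedy (visit rates only).** Take the variance of a patient's log rate as 1/(mT) + c², with m visits per month, T months, and an assumed between-patient CV c of 0.5 or 1.0.

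- Six months against 12, at 1 visit per month: standard error ratio √(1.167/1.083) = 1.04 (c = 1.0) to √(0.417/0.333) = 1.12 (c = 0.5).
- At 1 per 3 months: √(1.5/1.25) = 1.10 to √(0.75/0.5) = 1.22.
- At 1 per 6 months: √(2/1.5) = 1.15 to √(1.25/0.75) = 1.29.
- At 1 per 12 months: √(3/2) = 1.22 to √(2.25/1.25) = 1.34.
- Offset with a 12-month look-back, 15% to 60% recent switchers, 1 visit per 1 to 3 months: 0.1% to 2.5% larger.

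**The case against.** - **The arm-level effect at 12 months is modest.** That is right: 1.5 becoming 1.45 to 1.48 would rarely change a conclusion. But 12 months is not a rule in either document, and nothing stops a longer file from being totalled.
- **Tables 7 and 8 are examples, and totals are comparable under a common window.** The missing row units are weak evidence alone. A reader might infer that the arms' claims will cover different lengths of time; 12 months of SHL against six of EHL would give a ratio of 0.50 at identical monthly rates. The documents do not show this. Protocol 8.4 expects claims to vary in type and degree across insurers, which concerns content. Unequal coverage is possible, not documented. A common window longer than six months would still mix products.
- **Stand-alone documents may set a request period.** They may, and they are not in our copy. Attribution and scaling are analysis rules and belong in the SAP.
- **Treatment duration could enter as a covariate.** That neither removes pre-switch claims nor puts totals on a common time scale.
- **SAP 6.2.2 already warns that few patients may supply claims and that comparisons may be dropped.** This makes the inference conditional and counts against any remedy that discards patients. It does not cure the problem, because descriptive totals would mix products too.

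**Conclusion.** The point holds: as written, the claims comparison can count SHL use as EHL use in an outcome named in the primary objective, and no other section prevents it. With constant monthly rates the ratio is pulled towards 1. If use changes around the switch, the direction cannot be stated.

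The size, about 1.48 for a true 1.5 in hemophilia B and 1.45 to 1.48 in pooled hemophilia A, rests on the 12-month window, the even spread and the equal product mix, all assumptions. The share of recent switchers is not in the documents.

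Three stronger readings are not supported. A collapse in power to about 29% (d = 0.46 seen as 0.23) needs every EHL patient to be at the six-month minimum. The Adynovate-only figures match no planned comparison. Contamination of the SHL arm is possible but not documented.

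**What to change.** In SAP 4.1, 6.2.2 and 6.2.3, before claims are analysed:

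1. Count only claims with a service date on or after the start of the current product (derived from treatment duration) and within one stated look-back before the survey.
2. Record the start and end dates covered by each claims submission.
3. Analyse visits and costs per on-product month, with log(months of on-product coverage) as an offset in the GLMs, and report months of coverage by arm.
4. As a sensitivity analysis, use the six months before the survey, among patients whose claims cover them. Eligibility guarantees those months are on product, and this analysis does not assume use proportional to time.
5. Apply the same restriction to the descriptive tables if the low-numbers fallback is used.

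**Cost.** SAP wording and one added data item; Protocol 9.1 requires IRB/IEC and sponsor approval if consent wording changes. There are fewer claim-months. For visit rates, the offset raises the standard error by a few percent at most at 1 visit per 1 to 3 months. The six-month analysis raises it by 4% to 22% at those rates and about 15% to 34% at 1 visit per 6 to 12 months, frequencies listed in SAP Table 3. It also loses patients without full six-month coverage from a claims sample already expected to be incomplete. The precision cost for the four cost outcomes is not estimated, and the accuracy of the derived start date depends on the chart review form, which is not in our copy.
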